6.7 HANDLING OF MISSING DATA

The following guideline will be used when dealing with missing data related to the protocol-defined event in the primary efficacy endpoint. Patients who complete the treatment period will be considered as having a protocol-defined event if any of the following are reported during the 96-week *study*: at least one protocol-defined relapse, Gd-enhancing T1 lesions, new and/or enlarging T2 lesions, or CDP. Otherwise, the patient will be considered as being protocol-defined event free.

Patients who discontinue treatment early and have at least one event before early discontinuation will be considered as having a protocol-defined event. *Details of missing data handling for patients who discontinue treatment early and do not have any event before early discontinuation* will be specified in Statistical Analysis Plan.

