Appendix 1 Schedule of Activities (cont.)

Visit Number	Screening	Treatment Period						Safety Follow-up Visit ^b	Early Withdrawal Visit ^c	Unscheduled Visit (due to relapse) ^d
	1	2	3	4	5	6	7			
Week	-4 ^a	-	2	24	48	72	96			
Study Day (window in days)	-28	1 Baseline	15 (\pm 2)	169 (\pm 14)	337 (\pm 14)	505 (\pm 14)	673 (\pm 14)			
Brain MRI ^r		x ^s		x ^o	x ^o		x	x ^c		
Recording of potential relapses		x	x	x	x	x	x	x	x	x
Adverse event assessment ^t		x	x	x	x	x	x	x	x	x
Concomitant treatment review		x	x	x	x	x	x ^u	x	x	x
Methylprednisolone and antihistamine premedication ^v		x	x	x	x	x				
Ocrelizumab administration ^w		x	x	x	x	x				

β -hCG = beta human chorionic gonadotropin; eCRF = electronic Case Report Form; EDSS = Expanded Disability Status Scale; HBcAb = hepatitis B core antibody; HBsAg = hepatitis B surface antigen; HBV = hepatitis B virus; HepCAb = hepatitis C antibody; IRR = infusion-related reaction; IV = intravenous; MRI = magnetic resonance imaging; MS = multiple sclerosis; PCR = polymerase chain reaction; PML = progressive multifocal leukoencephalopathy; PRO = patient-reported outcome; QC = quality control.

^a The screening period will last up to 4 weeks, but it may be prolonged for up to 8 weeks for relevant clinical, administrative, or operational reasons.

^b The Safety Follow-up Period will begin when the patient *completes their infusion at Week 72 or discontinues from treatment early*. Patients will be assessed *at 24 weeks (at Week 96)*. If the peripheral blood B-cell count remains depleted *after 6 months from the date of the last infusion, the investigator may want to continue monitoring the B-cell count until it has returned to the baseline value or to the lower limit of the normal range, whichever is lower*. During the Safety Follow-up Period, patients who receive other B-cell targeted therapies will only be followed for an additional period of approximately 24 weeks from the start of the alternative MS treatment.

^c When a patient discontinues treatment, all assessments must be completed/obtained, except for MRI if done within the past 8 weeks unless clinically indicated.

Ocrelizumab—Genentech, Inc.

76/ Protocol MN30035, Version 5

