Appendix 1 **Schedule of Activities (cont.)**

- ^p Neurological examinations will be used to distinguish relapse in MS from another neurological (non-MS) disorder. Potential relapses should be recorded throughout the treatment period. Investigators will also screen patients for signs and symptoms of worsening neurological function localized to the cerebral cortex, such as cortical symptoms/signs, behavioral and neuropsychological alteration, retrochiasmal visual defects, hemiparesis, cerebellar symptoms/signs (e.g., gait abnormalities, limb incoordination). Patients with suspected PML should be withheld from ocrelizumab treatment until PML is ruled out by complete clinical evaluation and appropriate diagnostic testing (see Appendix 6). A patient with confirmed PML should be withdrawn from the study.
- ^q PRO assessments will consist of the following: Multiple Sclerosis Impact Scale 29 (MSIS-29), the Treatment Satisfaction Questionnaire for Medication (TSQM II), and the Treatment Satisfaction with Medicines Questionnaire (SATMED-Q). PROs completed at baseline should be in reference to the last-used DMT prior to enrollment. Please note that all PROs are required to be administered prior to administration of study drug and prior to any other study assessment(s) to ensure the validity of the instruments is not compromised.
- ^r Should only be done at scheduled visits unless PML is suspected.
- ^s MRI has to be conducted before the baseline visit, and results must be available prior to treatment. Prior to initiation of treatment on Day 1/Baseline, a QC report for the baseline MRI scan must have been received from the centralized reading center confirming scan passed QC. The brain MRI requires approximately 2 business days to be quality checked before dosing of ocrelizumab.

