#### **4.4 EFFICACY ANALYSIS**

Efficacy endpoints will be evaluated for the mITT or ITT population as specified. Sensitivity for primary endpoint will be conducted for the PP population.

For all change from baseline analyses, except for EDSS, baseline will be defined as the last non-missing value on or before the first infusion. Unless otherwise specified, the baseline EDSS will be defined as (1) the last non-missing value on or before the first infusion, for patients who were administered only one EDSS evaluation before the first infusion, or (2) the average of the 2 EDSS results pre infusion, for patients who were administered an additional evaluation in cases where the screening EDSS was more than 14 days prior to the first infusion.

The baseline EDSS will be rounded to the second decimal point. For analyses that stratify by analysis baseline EDSS i.e. ( $< 2.5$  vs.  $\geq 2.5$ ), the EDSS values will be rounded to the nearest one decimal value.

Per protocol, unscheduled MRI evaluations conducted for suspected PML will not be included in the analysis of efficacy endpoints.

Visit windows (defined in Module 2) will be applied to key efficacy assessments to accurately capture the timing of assessment.

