##### **4.4.1 Primary Efficacy Endpoint**

The proportion of patients who are free from a protocol-defined event during a 96-week period will be calculated and presented along with a two-sided 95% Clopper-Pearson exact confidence interval. Data from unscheduled visits within each respective 24-week interval will be included in the evaluation of the endpoint. Analyses will be performed for the mITT population. Patients are considered to have a protocol-defined event during the 96-week period if they discontinue due to lack of efficacy or death despite without a protocol-defined event as defined below.

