#### **4.4.2 Secondary Efficacy Endpoints**

The mITT population will be used for secondary efficacy endpoints of the proportion of patients free from a protocol-defined event during the first 24-week and 48-week period.

Analyses of all other secondary efficacy endpoints will be performed using the ITT population.

The proportion of patients free from a protocol-defined event during the first 24-week and 48-week will be presented along with a two-sided 95% Clopper-Pearson exact confidence interval. Same analysis method of the primary efficacy endpoint will be applied to the 24-week and 48-week outcomes. Note that event during the first 24-weeks will not include CDP events due to no confirmatory EDSS score can be observed within the first 24-weeks. A histogram of the percent of patients who are event free at weeks 24, 48, and 96 will be produced.

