### **Time-to-event endpoints**

The Kaplan–Meier method (i.e., the product limit estimator) will be used to estimate the time to onset of the 5 parameters listed below. Kaplan-Meier plots will be produced. The event-free probability at Week 96 will be calculated based on Kaplan-Meier method as sensitivity analyses of the primary endpoint, proportion of patients without a protocol-defined event.

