#### Time to protocol-defined event

For patient with an event, it will be defined as the earliest onset time of the following: a protocol-defined relapse, T1 Gd-enhanced lesion, new and/or enlarging T2 lesion, or confirmed disability progression (see below for the determination of the time to onset of confirmed disability progression)

Patients without an event (either during the complete 96-week study period, or before early withdrawal from treatment) will be censored at the last evaluation of a protocol defined event, i.e. the maximum time of last MRI or EDSS evaluation

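### A completer with no recorded event counts as event-free even if the Week 96 MRI is missing, and the planned sensitivity analyses do not test this when the Week 96 EDSS was done

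*Protocol*

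**What the plan says.** **The rule.** Protocol 6.7 gives a completer an event only if a relapse, a T1 Gd-enhancing lesion, a new or enlarging T2 lesion or confirmed disability progression (CDP) is reported. For everyone else: "Otherwise, the patient will be considered as being protocol-defined event free". It leaves to the SAP only those who stop treatment early without an event.

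**The scans.** Protocol 6.5.2 and Appendix 1 place post-baseline efficacy MRI at Weeks 24, 48 and 96, with none at Week 72. Appendix 1 says of MRI: "Should only be done at scheduled visits unless PML is suspected". SAP 4.4 adds that "unscheduled MRI evaluations conducted for suspected PML will not be included in the analysis of efficacy endpoints". SAP 4.4.1 does admit other unscheduled data ("Data from unscheduled visits within each respective 24-week interval will be included in the evaluation of the endpoint"), but under these limits that will rarely supply a scan. Early withdrawals are treated differently: "When a patient discontinues treatment, all assessments must be completed/obtained, except for MRI if done within the past 8 weeks unless clinically indicated".

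**The SAP's missing-data text.** The mITT set (SAP 4.1.2) removes event-free early discontinuers, except those who stopped for death or lack of efficacy. The missing-data text in SAP 4.4.1 deals with EDSS confirmation, and SAP 4.8 with adverse events and concomitant medication. None covers a missing scan.

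**The sensitivity analyses.** SAP 4.4.4 plans a per-protocol analysis, whose exclusions in Appendix 5 are eligibility violations, and a 50% imputation of progression first seen at Week 96. SAP 4.4.2 adds: "The event-free probability at Week 96 will be calculated based on Kaplan-Meier method as sensitivity analyses of the primary endpoint". In that analysis a patient without an event "will be censored at the last evaluation of a protocol defined event, i.e. the maximum time of last MRI or EDSS evaluation". It uses ITT: "Analyses of all other secondary efficacy endpoints will be performed using the ITT population".

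**The concern.** An unobserved outcome is scored as a success. A completer without the Week 96 scan has no MRI information for half of the 96 weeks, yet is reported as free of both lesion components over that time.

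The SAP handles missing scans elsewhere. The two lesion time-to-event endpoints censor at the last MRI, and the lesion counts use only patients with an interpretable scan at the visit. For the composite, the censoring date is the later of MRI and EDSS, so a Week 96 EDSS keeps an unscanned patient in the risk set to Week 96. The check then inherits the feature it should be testing.

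At stake is the accuracy of the headline proportion in a single-arm study. The confidence interval reflects sampling error only and does not show this.

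**Working it through.** **Planned precision.** Protocol 6.1 assumes 45% event-free and wants a 95% CI half-width of at most 4 points with 80% probability; it states n = 598.86, rounded to 600. Exact enumeration with a Wald interval gives a smallest n of 598, so the figure reproduces closely. At n = 600 the half-width is 1.96 × √(0.45 × 0.55 / 600) = 0.0398. The Clopper-Pearson interval for 270/600 is 41.0% to 49.1%.

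**Size of the shift.** The only documented inputs are N = 600 and 45%; the rest are assumptions.
- S48 = proportion event-free at Week 48: 0.55, 0.60 or 0.65
- c = 0.45 / S48 = chance of staying event-free to Week 96: 0.818, 0.750 or 0.692
- k = patients event-free at Week 48 who lack the Week 96 scan
- f = share of first events after Week 48 visible only on MRI

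Shift = k × (1 − c) × f / 600. Example: 18 × 0.25 × 1 / 600 = 0.75 points. With f = 1:

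| k | S48 = 0.55 | 0.60 | 0.65 |
|---|---|---|---|
| 18 (3% of 600) | 0.55 | 0.75 | 0.92 |
| 30 (5% of 600) | 0.91 | 1.25 | 1.54 |
| 3% of those event-free at Week 48 (9.9 / 10.8 / 11.7) | 0.30 | 0.45 | 0.60 |
| 5% of those event-free at Week 48 (16.5 / 18 / 19.5) | 0.50 | 0.75 | 1.00 |

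f = 0.5 halves every entry. The range is therefore about 0.15 to 1.5 points.

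**Bounds.** With S48 = 0.60 and k = 18, 342 × 0.75 = 256.5 scanned patients are event-free. Counting the 18 as events gives 256.5/600 = 42.75%; counting them event-free gives 274.5/600 = 45.75%. For k = 30 the bounds are 41.25% and 46.25%. The gap is always k/600.

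**Direction against the true value.** Assume 10% dropout spread evenly over 96 weeks, S24 = 0.70, S48 = 0.60, true S96 = 0.45, f = 1, and no scan at withdrawal. Per 100 patients:
- 90 complete, of whom 90 × 0.45 = 40.5 are event-free.
- Dropouts with an event already seen stay in mITT: 2.5 × 0 + 2.5 × 0.30 + 5 × 0.40 = 2.75.
- With all scans, mITT gives 40.5 / 92.75 = 43.7%.
- If 5% of the 54 completers event-free at Week 48 are unscanned (2.7), the hidden events are 2.7 × 0.25 = 0.675, and mITT gives 41.175 / 92.75 = 44.4%.

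Simulation gave 43.6% and 44.4%. With a withdrawal MRI it gave 43.2% and 43.9%. The rule raises the figure, but it stays below the assumed 45%.

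**Kaplan-Meier check, same scenario.**
- Planned censoring: 54 at risk after Week 48, with 51.3 × 0.25 = 12.825 events seen. 0.60 × (1 − 12.825/54) = 45.75%, a shift of +0.75.
- Censoring at last MRI, f = 1: 0.60 × 0.75 = 45.0%, no shift.
- Censoring at last MRI, f = 0.5: relapse or progression in unscanned patients still counts, 2.7 × 0.125 = 0.3375. 0.60 × (1 − 13.1625/51.6375) = 44.7%, a shift of −0.29. Planned censoring gives 0.60 × (1 − 13.1625/54) = 45.4%, a shift of +0.38.
- Visits spread over ±14 days, f = 0.5 (simulation; 3%, 5% and 8.3% of Week 48 event-free completers unscanned): +0.14, +0.23, +0.40 under planned censoring; −0.23, −0.38, −0.65 under last-MRI censoring.

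**The case against.** **The Kaplan-Meier analysis already departs from the rule.** This is partly right. If the whole Week 96 visit is missed, censoring falls at the last EDSS, typically Week 72. A reader might infer that no planned analysis touches missing Week 96 data at all; the SAP does not support that. The gap is a Week 96 EDSS without a Week 96 MRI.

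**The rule may move the estimate toward the truth.** This stands. A reader might infer that the reported proportion will be too high. The plan supports only an upward shift relative to the same mITT analysis with complete scans. mITT drops event-free early discontinuers and keeps those with events, which pulls the other way.

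**Censoring at the last MRI is no clear improvement.** This also stands. It did better in some runs, but in the ±14-day runs with f = 0.5 its error exceeded the one it removes. It should not replace the planned rule.

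**Scan availability will be visible anyway.** The lesion summaries use patients with interpretable scans, so missing scans will show there. They will not show how many belong to patients counted as event-free.

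**Unseen documents may settle it.** DAP Module 2 and the imaging charter were not supplied and could contain a rule. One that decides the primary outcome still belongs in the SAP's primary-endpoint section.

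**Conclusion.** The point holds as a minor one. The stated rule counts a missing Week 96 scan as no event on two of four components, and no planned sensitivity analysis tests this when the Week 96 EDSS was done.

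The true size is unknown. The 0.15 to 1.5 points rest on assumed missing-scan rates of 3–5%, 55–65% event-free at Week 48, a true 96-week value of 45%, and f between 0.5 and 1. That is well inside the planned half-width of 4. Protocol section 6 describes a mostly descriptive single-arm study, and no success threshold is set, so no pass/fail decision depends on it. The 3- and 5-point gaps between bounds come from scoring every unscanned patient as an event; they are limits, not expected bias.

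A separate wording problem touches the same rule. The treatment period is 72 weeks in the Protocol Synopsis, Protocol 3.1 and both synopsis copies in the SAP, but ends at Week 96 in Protocol 3.6, SAP section 2 and the end-of-study text of the synopses. A reader might infer that a patient with no Week 96 visit is a completer. SAP 4.2 and the exposure definition in SAP 4.4.2 work to Week 96, which argues against that reading, but the passages disagree.

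**What to change.** In SAP 4.4.4, keeping the primary rule and mITT membership unchanged:

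1. Report how many patients counted as event-free lack an interpretable Week 96 MRI.
2. Add a sensitivity analysis giving the primary proportion, with Clopper-Pearson CI, with these patients counted as event-free (the current rule) and as having an event. For illustration, if 30 of 270 event-free patients among 600 lacked the scan, the pair would be 45.0% (41.0% to 49.1%) and 240/600 = 40.0% (36.0% to 44.0%).
3. Optionally, show the composite Kaplan-Meier estimate censored at last MRI beside the planned version, not in its place, and note that it can err low by more than the bias it removes.

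Separately, reconcile the 72-week and 96-week descriptions of the treatment period.

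The cost is SAP wording, one count and one pair of proportions, all from data already collected. The efficacy definition needs no protocol amendment; the protocol's period labels can be aligned at the next one. The downside is a little more analysis work and a lower bound that may look less favourable.

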6.8 INTERIM ANALYSES

It is estimated that two to three interim analyses will be performed during the course of the study, according to patient enrollment and availability of data of interest. Interim analyses may be used for internal decision making, hypothesis generation, abstraction/publication for major MS conferences, or other purposes, as applicable. Details on the timing and scope of interim analyses will be described in the Statistical Analysis Plan.

7. DATA COLLECTION AND MANAGEMENT

7.1 DATA QUALITY ASSURANCE

The Sponsor will supply eCRF specifications for this study. A contract research organization (CRO) will be responsible for data management of this study, including quality checking of the data. Data entered manually will be collected via EDC through use of eCRFs. Sites will be responsible for data entry into the EDC system. In the event of discrepant data, the CRO will request data clarification from the sites, which the sites will resolve electronically in the EDC system.

Ocrelizumab—Genentech, Inc.
65/ Protocol MN30035, Version 5

The CRO will produce a Data Quality Plan that describes the quality checking to be performed on the data. Local laboratory data will be sent directly to the CRO, using the CRO's standard procedures to handle and process the electronic transfer of these data.

The Sponsor will perform oversight of the data management of this study, including approval of the CRO's data management plans and specifications. Data will be periodically transferred electronically from the CRO to the Sponsor, and the Sponsor's standard procedures will be used to handle and process the electronic transfer of these data.

eCRFs and correction documentation will be maintained in the EDC system's audit trail. System backups for data stored at the CRO and records retention for the study data will be consistent with the CRO's standard procedures.

7.2 ELECTRONIC CASE REPORT FORMS

eCRFs are to be completed through use of a Sponsor-designated EDC system. Sites will receive training and have access to a manual for appropriate eCRF completion. eCRFs will be submitted electronically to the Sponsor and should be handled in accordance with instructions from the Sponsor.

All eCRFs should be completed by designated, trained site staff. eCRFs should be reviewed and electronically signed and dated by the investigator or a designee.

At the end of the study, the investigator will receive patient data for his or her site in a readable format on a compact disc that must be kept with the study records. Acknowledgement of receipt of the compact disc is required.

7.3 SOURCE DATA DOCUMENTATION

Study monitors will perform ongoing source data verification to confirm that critical protocol data (i.e., source data) entered into the eCRFs by authorized site personnel are accurate, complete, and verifiable from source documents.

Source documents (paper or electronic) are those in which patient data are recorded and documented for the first time. They include, but are not limited to, hospital records, clinical and office charts, laboratory notes, memoranda, patient-reported outcomes, evaluation checklists, pharmacy dispensing records, recorded data from automated instruments, copies of transcriptions that are certified after verification as being accurate and complete, microfiche, photographic negatives, microfilm or magnetic media, X-rays, patient files, and records kept at pharmacies, laboratories, and medico-technical departments involved in a clinical trial.

Before study initiation, the types of source documents that are to be generated will be clearly defined in the Trial Monitoring Plan. This includes any protocol data to be

Ocrelizumab—Genentech, Inc.
66/ Protocol MN30035, Version 5

entered directly into the eCRFs (i.e., no prior written or electronic record of the data) and considered source data.

Source documents that are required to verify the validity and completeness of data entered into the eCRFs must not be obliterated or destroyed and must be retained per the policy for retention of records described in Section [7.5](#).

To facilitate source data verification, the investigators and institutions must provide the Sponsor direct access to applicable source documents and reports for trial-related monitoring, Sponsor audits, and IRB/EC review. The study site must also allow inspection by applicable health authorities.

7.4 USE OF COMPUTERIZED SYSTEMS

When clinical observations are entered directly into a study site's computerized medical record system (i.e., in lieu of original hardcopy records), the electronic record can serve as the source document if the system has been validated in accordance with health authority requirements pertaining to computerized systems used in clinical research. An acceptable computerized data collection system allows preservation of the original entry of data. If original data are modified, the system should maintain a viewable audit trail that shows the original data as well as the reason for the change, name of the person making the change, and date of the change.

7.5 RETENTION OF RECORDS

Records and documents pertaining to the conduct of this study and the distribution of IMP, including eCRFs, electronic PRO data (if applicable), Informed Consent Forms, laboratory test results, and medication inventory records, must be retained by the Principal Investigator for at least 15 years after completion or discontinuation of the study, or for the length of time required by relevant national or local health authorities, whichever is longer. After that period of time, the documents may be destroyed, subject to local regulations.

No records may be disposed of without the written approval of the Sponsor. Written notification should be provided to the Sponsor prior to transferring any records to another party or moving them to another location.

